9.2.2.5 Potential Wound Complications

Sponsor will review all AEs to identify potential wound complications (eg., wound infections, systemic infections, wound complications, surgical treatments of the wound).

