### **4.2.2. Secondary endpoints**

- Wound infection, both for the primary and the secondary lesions

- Systemic infection
- Surgical treatment of the wound
- Hospitalisation defined as being admitted for >24 hours
- Course of the secondary lesions defined clinically as for the primary [49]
- Change in pain from week 0 to 12 according to 100 mm Visual Analog Pain Scale (VAS)
  - Pain scale done at Screening, weeks 1, 2, 4, 6, 8, 10, 12, and EOS (FU) visit
- Change in dose and type of pain medication assessed as a continuous variable. Name (INN), dose, and number of pills captured.
- Wound QOL score done at Screening and weeks 1, 6, and 12
- Death

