#### 5.5. Patient Withdrawal and Replacement

A patient is defined as having entered the clinical trial when he/she has provided written informed consent. A withdrawal is a patient who receives a study patient code and for whom treatment is prematurely terminated for any reason.

Possible reasons for withdrawal of a subject from the clinical trial:

- Subject does not fulfil inclusion criteria
- AE(s)
- Withdrawal of consent
- Subject lost to follow-up
- Protocol violation
- Pregnancy
- Other reasons as judged by the investigator (see also 7.1.4 12-Lead Electrocardiogram abnormalities)

Patients may withdraw consent for participation in the clinical trial at any time without penalty and for any reason without prejudice to his or her future medical care. The patient does not need to give a reason for withdrawal of consent. The

Investigator is also free to terminate a patient's involvement in the clinical trial at any time, if the patient's clinical condition or non-compliance warrants it. The Sponsor or the Regulatory Authorities may request termination of the clinical trial if there are concerns about study conduct or safety.

In all cases, the reason(s) for withdrawal and the primary reason or failure to provide a reason, must be recorded in the Case Report Form (CRF).

If a patient is withdrawn, or chooses to withdraw, from the clinical trial for any reason, the Investigator must make every possible effort to perform the evaluations described for the End of Study Visit (see Section 8.2.5) or to verify the health status of the patient by calling the national death registry. Withdrawn patients may not re-enter the clinical trial.

Entered patients who leave the clinical trial before receiving a study patient code will be considered as screening failures and will be replaced.

Patients who are withdrawn from the study may be replaced at the discretion of the Sponsor and Principal Investigator. Replaced patients will receive the whole treatment.

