### 7.1.2.2. Definitions

An adverse event (AE) is any unfavourable and unintended sign, symptom, or disease that appears or worsens in a subject or clinical investigation subject during the period of observation in a clinical study.

The adverse event may be any of the following:

- A new illness,
- An exacerbation of a sign or symptom of the underlying condition under treatment or of a concomitant illness (including abnormal laboratory finding)
- Unrelated to participation in the clinical study or an effect of the study medication or comparator drug, or
- A combination of one or more of the above factors.

No causal relationship with the study medication is implied by the use of the term “adverse event.” An exacerbation of a pre-existing condition/illness is defined as a more frequent occurrence or as an increase in the severity of the pre-existing condition/illness during the study. Planned or elective surgical or invasive procedures for pre-existing conditions that have not worsened are not adverse events. However, any complication that occurs during a planned or elective surgery is an adverse event. (If the event fits the seriousness criteria, such as an extended hospitalisation, it will be considered a serious adverse event.) Conditions leading to unplanned surgical procedures may be adverse events.

In order for the Sponsor to collect additional information about the clinically important laboratory or diagnostic tests (eg, blood, urinalysis, ECG, imaging) abnormalities, at a minimum, the following abnormalities should be captured on the AE CRF:

- Any test result that meets the criteria for a SAE
- Any test abnormality that suggests a disease and/or organ toxicity that is new or has significantly worsened
- Any test abnormality that required the subject to have study medication discontinued or interrupted

- Any test abnormality that required the subject to receive specific corrective therapy, close observation, more frequent follow-up assessment, or further diagnostic investigation

Laboratory test abnormalities may not be of clinical significance in the absence of:

- Clinical symptoms
- Change in lifestyle
- Need for intervention

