#### **7.1.2.3.1. Seriousness**

A SAE is defined as any untoward medical occurrence that at any dose:

- Results in death
- Is life-threatening; this means that the patient was at risk of death at the time of the event; it does not mean that the event hypothetically might have caused death if it were more severe
- Requires hospitalisation or prolongation in existing hospitalisation
- Results in persistent or significant disability or incapacity
- Is a congenital anomaly or a birth defect
- Is an important medical event that may not result in death, be life threatening, or require hospitalization, but may be considered an SAE when, based upon appropriate medical judgment, it may jeopardize the subject and may require medical or surgical intervention to prevent one of the outcomes listed in this definition

Examples of such events are invasive or malignant cancers, intensive treatment in an emergency room or at home for allergic bronchospasm, blood dyscrasias or convulsions that do not result in hospitalisation, or development of drug dependency or drug abuse.

Note that an AE or suspected adverse reaction is considered “life-threatening” for reporting as an SAE if, in the view of either the Investigator or the Sponsor, its occurrence places the subject at immediate risk of death. It does not include an AE or suspected adverse reaction that, had it occurred in a more severe form, might have caused death.

The following events do not meet the definition of an SAE with regard to hospitalization: planned hospitalization for a condition present prior to the subject’s enrolment in the study, hospitalization of the subject for compliance/convenience reasons, planned hospitalization for an elective medical/surgical procedure, scheduled treatments, or routine check-ups, or a hospitalization or an emergency room visit lasting less than 24 hours.

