#### **7.1.2.4. Recording of Adverse Events**

Adverse events will be collected from the time a patient signs the ICF until the Follow-up Visit.

All AEs, regardless of the relationship to IMP, must be recorded in the source documents (e.g., medical record) and will be recorded on the appropriate CRF pages, and documents provided by the Sponsor.

All AE reports should contain a brief description of the event, date, and time of onset, date and time of resolution, intensity, treatment required, relationship to IMP, action taken with the IMP, outcome, and whether the event is classified as serious.

Serious adverse events should be collected for up to 30 days after the last dose of the IMP for subjects unless the subject has withdrawn consent. This could be collected as a phone call.

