5.2.2 Secondary endpoints

Wound healing:

- Absolute change from baseline in BWAT total and component scores by visit for the primary lesion, secondary lesion, and tertiary lesions.
- Qualitative change from baseline in imaging score by visit for the primary lesion, secondary lesion, and tertiary lesions.

Pain:

- Absolute change from baseline by visit in the Pain Visual Analog Scale (VAS).

Quality of Life:

- Absolute change from baseline at Weeks 6 and 12 in global score and subscales of wound QoL score.

Wound and disease complications:

- Presence/absence of new wound infection at any time post baseline
- Presence/absence of new systemic infection at any time post baseline
- Surgical treatment of the wound at any time post baseline
- Requires or prolongs hospitalization
- Death

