9.2.3 Hospitalization and Death

Hospitalizations will be identified from the list of Adverse Event for which Seriousness has been reported as “Requires or prolongs hospitalization”.

The number and percentage Hospitalizations will be summarized by System Organ Class and Preferred Term presenting the number of events, the number of subjects and percentage (Shell T-5).

Deaths will be identified from the list of adverse events, for which Seriousness has been reported as “Results in death” or Outcome has been reported as ”Death” or Primary Reason for Premature Termination has been reported as “Death” on the End of Study CRF section.

The number and percentage of deaths will be computed and will be summarized by System Organ Class and Preferred Term (Shell T-5).

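### Wound surgery and hospitalisation are sourced only from adverse events, so planned wound surgery and planned admissions that meet the protocol endpoints can be missed; for death the gap is narrower

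*SAP*

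**What the plan says.** **Surgery.** Protocol 4.2.2 lists surgical treatment of the wound as a secondary endpoint without qualification. SAP 5.2.2 words it as "Surgical treatment of the wound at any time post baseline". The only source the SAP names is in 9.2.2.5: "Sponsor will review all AEs to identify potential wound complications (eg., wound infections, systemic infections, wound complications, surgical treatments of the wound". Protocol 7.1.2.2 states: "Planned or elective surgical or invasive procedures for pre-existing conditions that have not worsened are not adverse events".

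**Hospitalisation.** Protocol 4.2.2 gives the endpoint as "Hospitalisation defined as being admitted for >24 hours". SAP 5.2.2 replaces this with the seriousness criterion of requiring or prolonging an admission, and SAP 9.2.3 follows: "Hospitalizations will be identified from the list of Adverse Event for which Seriousness has been reported as" meeting that criterion. Protocol 7.1.2.3.1 lists admissions that are not serious adverse events (SAEs). The list includes planned admission for a condition present before enrolment, admission for compliance or convenience, and "planned hospitalization for an elective medical/surgical procedure, scheduled treatments, or routine check-ups".

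**Death.** SAP 9.2.3 uses three fields: AE seriousness, AE outcome, and the primary reason for premature termination on the End of Study CRF page. Protocol 7.1.2.4 has SAEs collected "for up to 30 days after the last dose of the IMP for subjects unless the subject has withdrawn consent". For withdrawn patients, Protocol 5.5 asks sites to attempt the End of Study evaluations or to "verify the health status of the patient by calling the national death registry".

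**Declared changes.** SAP section 10 has one entry against 5.2.2, and it concerns pain medication. It does not mention surgery, hospitalisation or death.

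**The concern.** The endpoints are defined by what happened to the patient: an operation on the wound, an admission over 24 hours, a death. For the first two, the data source is defined by something else, namely whether the event qualifies as an AE or SAE. Where the AE rules exclude an event that the endpoint includes, an analyst who follows the SAP exactly will not count it. The tables would still be read as rates of wound surgery and hospitalisation as the protocol defines them. Each such omission can only lower the count, and a single-arm trial has no control group in which the same omission would occur.

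**Working it through.** The plan gives no figure for these endpoints, so the check sets each definition beside its source and the rule that governs the source.

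1. **Surgery.** The endpoint covers any surgical treatment of the wound after baseline. The source is the AE list. A planned or elective procedure for a pre-existing condition that has not worsened is not an AE. The target ulcer is present at entry, so planned surgery on it while it has not worsened meets the endpoint and is excluded from the only named source. For unplanned surgery, Protocol 7.1.2.2 says the condition leading to it may be an AE; the procedure itself is not named as one.

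2. **Other routes for surgery.** The schedules (Protocol Table 1, SAP Table 001) have no row for wound procedures. Protocol 6.8.1 covers medicinal products only. Protocol 7.1.1 records past surgery at screening, not surgery on study. Wound surgery is foreseeable: Protocol 4.1 says local wound care may involve surgeons, and Protocol 2.2 lists surgical debridement among empirical treatments.

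3. **Hospitalisation.** The protocol endpoint covers any admission over 24 hours. The source is AEs flagged for hospitalisation. A planned admission of several days meets the first and is excluded from the second by Protocol 7.1.2.3.1.

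4. **Size for surgery and hospitalisation.** Assuming 15 dosed patients, one missed patient is 1/15 = 6.7 percentage points. With exact (Clopper-Pearson) 95% intervals, 0/15 gives 0 to 21.8%, 1/15 gives 0.2 to 31.9%, and 2/15 = 13.3% gives 1.7 to 40.5%. The documents give no basis for the number missed.

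5. **Death.** A death can escape all three fields in SAP 9.2.3 only if the termination reason is something other than death and the death falls after consent withdrawal or more than 30 days after the last dose. As an illustration, assume a constant hazard from the 45% one-year survival in Protocol 2.2 and counting to Week 13 (day 91):
   - Daily hazard: h = -ln(0.45)/365.25 = 0.00219.
   - Last dose at Week 4 (day 28), consent kept: uncovered days = 91 - 28 - 30 = 33; 1 - exp(-33h) = 7.0%. For a last dose at Week 2 this is 9.8% (47 days); at Week 8, 1.1% (5 days).
   - Consent withdrawn at Week 4: uncovered days = 91 - 28 = 63; 1 - exp(-63h) = 12.9%. At Week 2 this is 15.5% (77 days); at Week 8, 7.4% (35 days).
   - With 50% one-year survival, the two Week 4 figures become 6.1% and 11.3%.
   
   These are risks for one patient who stops early, not for the trial. For a patient dosed through Week 12, 30 days after the last dose runs past Week 13, so no gap arises if consent is kept.

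6. **SAE period.** Protocol 7.1.2.4 collects SAEs to 30 days after the last dose; Protocol 7.1.2.5 sets the reporting period from first dose to the Follow-up Visit. These are different end points, and step 5 uses the 30-day one.

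**The case against.** SAP 5.2.2 groups these endpoints under wound and disease complications, and within the SAP sections 5.2.2 and 9.2.3 agree on hospitalisation. Leaving planned or convenience admissions out of a complications endpoint is defensible. That stands as a choice, but it departs from Protocol 4.2.2 and section 10 does not say so.

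The surgery exclusion is conditional. It needs a planned or elective procedure and a condition that has not worsened. Complications of elective surgery are AEs, and so are exacerbations of the underlying disease. Protocol 7.1.2.3.1 also leaves out hospital stays under 24 hours, which broadly matches the 24-hour threshold in Protocol 4.2.2. All of this stands and limits the gap to planned events.

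The CRF is not available, and SAP section 4 refers readers to it for data collection. It may record procedures or admissions on a separate page. A reader might infer that these endpoints are undercounted in fact; the documents support only that they can be. A reader might also infer a bias in the drug's favour. The omissions do lower counts, but the plan sets no historical rate or test for surgery or admissions, and the primary endpoint is unaffected.

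On death, a reader might infer that every death after withdrawal is lost. It is not: the End of Study termination reason lies outside the AE fields, and stopping treatment does not stop SAE collection. Nor is the mortality implied over 12 weeks (1 - 0.45^(12/52) = 16.8%, or 2.5 of 15) the size of the gap. That is expected total mortality, most of which the SAP's sources would record.

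**Conclusion.** The point holds for surgery and hospitalisation. The SAP's stated sources omit planned surgery on a non-worsened target ulcer and planned admissions over 24 hours. Both meet Protocol 4.2.2, and the narrowing is not declared. This goes beyond missing detail, because the sourcing rule conflicts with the endpoint definition. The size is unknown at 6.7 percentage points per missed patient, and there may be no loss if the CRF records these events and the analysis uses them.

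For death the point holds only for patients who stop early, as in step 5 of the working. Those percentages rest on a constant hazard. The true risk could be lower, since entry excludes patients without a reasonable expectation of surviving beyond 6 months, or higher, since Protocol 2.2 reports the largest survival difference in the first months after diagnosis. The protocol already provides a vital-status check that could find some of these deaths, but SAP 9.2.3 does not use it. The SAE periods in Protocol 7.1.2.4 and 7.1.2.5 must be reconciled.

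These are descriptive secondary endpoints, so this should be corrected but does not touch the primary analysis.

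**What to change.** - **SAP 9.2.2.5:** derive surgical treatment of the wound from all wound procedures recorded after the first dose, in the CRF or source records, whether or not they are AEs. If the CRF already holds them, naming that page is enough.
- **SAP 9.2.3, hospitalisation:** count every admission over 24 hours as Protocol 4.2.2 defines it, and show SAE hospitalisations as a subset.
- **SAP 9.2.3, death:** add the Protocol 5.5 vital-status check as a source, counted to a fixed date (Week 13 from first dose) for all dosed patients, as consent and local law allow. State the denominator: the table in SAP 8.2.4 assigns secondary endpoints to the Intention to Treat set, which also requires a post-baseline efficacy measurement.
- **Protocol 7.1.2.4 and 7.1.2.5:** reconcile the SAE periods.
- **SAP section 10:** declare the definitions used. If data outside the AE list cannot be retrieved, relabel the endpoints as AE-reported wound surgery and SAE hospitalisation and declare that here.

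The cost is SAP wording plus either source-record queries or a change to a paper CRF. Parts of the SAP describe study conduct in the past tense, so for patients already treated, queries may be the only route. Event counts may come out somewhat higher.

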9.2.3 Hospitalization and Death

Hospitalizations will be identified from the list of Adverse Event for which Seriousness has been reported as “Requires or prolongs hospitalization”.

The number and percentage Hospitalizations will be summarized by System Organ Class and Preferred Term presenting the number of events, the number of subjects and percentage (Shell T-5).

Deaths will be identified from the list of adverse events, for which Seriousness has been reported as “Results in death” or Outcome has been reported as ”Death” or Primary Reason for Premature Termination has been reported as “Death” on the End of Study CRF section.

The number and percentage of deaths will be computed and will be summarized by System Organ Class and Preferred Term (Shell T-5).

9.2.4 Exploratory Analyses

9.2.4.1 Absolute change in BWAT total score between Week 12 and Follow-up for all lesions.

The absolute change in BWAT total score of the primary lesion between Week 12 and Follow-up will be summarized using the missing imputation method specified for the primary endpoint.

The same analysis will also be done for the secondary and tertiary lesions if there is enough data.

9.2.4.2 BWAT vs VAS correlation.

Correlation between VAS and BWAT (absolute and relative) change from baseline to Week 12 will be assessed:

- Absolute VAS change from baseline vs absolute BWAT change from baseline
- Relative VAS change from baseline vs relative BWAT change from baseline

Correlation will be assessed graphically by means of linear regression analysis where VAS and BWAT will be considered as dependent and independent variables, respectively. Linear regression parameters, correlation estimate and their 95% confidence intervals will be presented.

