8.4 Missing data

This section provides a general description about methods used to impute missing data. Specific details for imputed variables will be given in Section 9.2.

Missing imputation will be only applied for the primary and key secondary endpoints, i.e. BWAT, VAS and Wound QoL. The main analysis will be based on Multiple Imputation (MI). Sensitivity analyses will be conducted to assess the robustness of the results with regards to handling of missing data. The following methods will be applied: Last Observation Carried Forward (LOCF), and Observed Cases (OC) (Molenberghs & Kenward, 2007).

Multiple Imputation

Multiple imputation was selected as the method for imputing missing data as the natural progression of calciphylaxis skin lesions under standard of care treatment varies considerably [Nigwekar et al, 2013]. Rather than making assumptions under the LOCF method that may either be too optimistic or conservative relative to the natural progression of skin lesions under standard

of care treatment, multiple imputation uses all available data for a given variable to impute for missing data. Missing data will be imputed 100 times to generate 100 complete data sets, using the MI SAS procedure (using *Markov Chain Monte Carlo (MCMC)* for continuous variables or the *Fully Conditional Specification (FCS) Discriminant* analysis for categorical variables). The absolute change from baseline at Week 12 will be then derived from observed and imputed data at this time point. The 100 complete data sets will be then analyzed using a paired t-test, and the MIANALYZE procedure will be used to generate valid statistical inferences by combining results from the 100 analyses using Rubin's formulae.

The number of imputations (100) will be informally verified by replicating sets of 100 imputations and checking whether the combined results are stable. If not stable, the number of imputations will be increased and informally checked as above, and thus until stable estimates are obtained.

The imputation model will include:

- The endpoint values from all non-missing scheduled weeks.
- The endpoint values from other items within the same scale, if applicable.

LOCF

This analysis imputes the last measured value of the endpoint to all subsequent evaluations. In case of missing data at baseline, the missing value will be imputed using the first available visit, i.e., First Observation Carried Backward, FOCB.

Observed Cases

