9.2 Efficacy Analysis

9.2.1 Primary endpoint

The primary endpoint is the absolute change in BWAT total score between baseline (Week 1) and Week 12 for the primary lesion (the largest one).

Absolute change from baseline will be calculated as differences in the total score from Week 1 to Week 12. Descriptive statistics will be presented. Differences between the two visits will be analyzed using a Paired Student's T-Test. (Shell T-7)

Missing imputation will be done on the item level. For the imputation of baseline missing item scores FOCB will be used for LOCF imputation method if any subsequence item score is available, else the score will be imputed by 3. For the multiple imputation method the baseline values will be imputed by 3. The main analysis will be done using Multiple Imputation, and supported by the different sensitivity analysis as specified in Section 8.4. A forest plot summarizing these results will be produced presenting the estimated change from Week 1 to Week 12 and its 95% confidence interval for the different imputation methods (Shell F - 1).

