9.2.2 Secondary endpoints

9.2.2.1 *Change from baseline in BWAT total and component scores by visit*

BWAT Score is collected at Week 1, Week 2, Week 4, Week 6, Week 8, Week 10, Week 12 and Follow-up. Differences in absolute and relative change from baseline will be also presented. Differences from baseline will be tested using a Paired Student's T-Test. (Shell T-7). Additionally, a figure presenting the evolution (mean, and 95% confidence interval) of the total score and

individual items by visit will be presented (Shell F-2). This analysis will be done using Observed Cases.

9.2.2.2 *The previous analysis will also be done for the secondary and tertiary lesions if there is enough data. Change from baseline in imaging score by visit*

Image evaluation will be summarized separately for the blinded and unblinded reviews. Percentages for each category and their exact 95% confidence interval (Clopper-Pearson) will be presented. Imputation methods will not be used for this score.

9.2.2.3 *Change from baseline in the Pain Visual Analog Scale (VAS) by visit*

Absolute change from baseline will be calculated as differences in the total score from Week 1 to Week 12. Descriptive statistics will be presented. Differences between the two visits will be analyzed using a Paired Student's T-Test. (Shell T-7)

The Week 1 to Week 12 analysis will be done using Multiple Imputation, and supported by the different sensitivity analysis as specified in Section 8.4. A forest plot summarizing these results will be produced presenting the estimated change from baseline and 95% confidence interval for the different imputation methods. These analysis will also be done for the PP population.

Additionally, the VAS Score is collected at Screening, Week 1, Week 2, Week 4, Week 6, Week 8, Week 10, Week 12 and Follow-up. VAS scores will be summarized by visit. Differences in absolute and relative change from Week 1 to each visit will be presented descriptively. Finally, differences in absolute change from Week 12 to Follow-up will be summarized. Statistically significant differences from the reference values will be tested using a Paired Student's T-Test (Shell T-7). Additionally, a figure presenting the evolution (mean, and 95% confidence interval) of the VAS score by visit will be presented (Shell F-2). This analysis will be done using Observed Cases.

9.2.2.4 *Change from baseline in total and subscales of wound QoL score by visit*

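### SAP 9.2.4.1 imputes the exploratory Week 12 to Follow-up BWAT change without requiring that either visit took place, while the same contrast for pain VAS uses observed cases

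*SAP*

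**What the plan says.** SAP 9.2.4.1, under the exploratory analyses, states that the Week 12 to Follow-up change in BWAT total score of the primary lesion "will be summarized using the missing imputation method specified for the primary endpoint". The same is planned for secondary and tertiary lesions if data allow.

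For the primary endpoint, SAP 9.2.1 says "Missing imputation will be done on the item level" and "The main analysis will be done using Multiple Imputation, and supported by the different sensitivity analysis as specified in Section 8.4". SAP 8.4 names the sensitivity methods as LOCF and Observed Cases. It describes LOCF as follows: "This analysis imputes the last measured value of the endpoint to all subsequent evaluations". The imputation model contains "The endpoint values from all non-missing scheduled weeks" and, where applicable, the other items of the scale. The only change that SAP 8.4 derives from the imputed data is the one from baseline: "The absolute change from baseline at Week 12 will be then derived from observed and imputed data at this time point".

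For pain VAS, SAP 9.2.2.3 plans that "differences in absolute change from Week 12 to Follow-up will be summarized" and closes that paragraph with "This analysis will be done using Observed Cases". SAP 9.2.2.1 puts the by-visit BWAT results, which include Week 12 and Follow-up, on observed cases too.

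**The concern.** Under the schedule, Week 12 ends treatment and Follow-up is Week 13. The contrast between them describes what the lesion does once SNF472 stops, so it has a direct meaning only for a patient who was treated to Week 12 and seen afterwards. A patient who died or withdrew earlier has no such change to estimate. SAP 9.2.4.1 nevertheless fills one in, and does the same for a patient who reached Week 12 but missed Follow-up.

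What is at stake is the reading of an exploratory result. Part of the reported off-treatment change would come from the imputation and not from any observation. The result would also be on a different basis from the matching VAS contrast and from the by-visit BWAT table beside it.

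**Working it through.** **1. The plan's own figure.** The documents give no expected change, standard deviation or dropout rate for this contrast. The only design figure is 15 patients for 60% against 25% with 80% power. It reproduces closely: an exact binomial rule of at least 8 of 15 has one-sided type I error 0.0173 and power 0.787. The point does not depend on it; 15 is used below only as an illustrative n.

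**2. Who enters.** SAP 9.2.4.1 sets no completion condition, and the table of analysis sets in SAP 8.2.4 has no row for exploratory analyses. The Intention to Treat Set needs one dose and one post-baseline efficacy measurement, so early dropouts qualify. Even the Per Protocol Set needs only 75% of doses: 0.75 × 36 = 27 infusions, which is 9 weeks at three per week.

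**3. What each method does.**

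| Patient's BWAT record | Multiple imputation (main) | LOCF | Observed cases |
|---|---|---|---|
| Week 12 and Follow-up done | observed change | observed change | observed change |
| Week 12 done, no Follow-up | Follow-up generated | 0 | left out |
| Nothing at Week 12 or later | both scores generated | 0 | left out |
| Left before Week 12, End of Study score held as Follow-up | Week 12 generated | End of Study score minus last earlier score | left out |

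Multiple imputation does condition on the patient's own earlier scores. It has no term for withdrawal, death or treatment status. What it supplies for the step after treatment therefore rests on the patients in whom that step was seen.

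**4. Size under LOCF.** Let n patients be analysed, of whom k fall in the two rows that give 0. Let m be the mean change in the other n − k.

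LOCF mean = [(n − k) × m + k × 0] / n = m × (n − k)/n

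With n = 15 this gives 13/15 = 0.867 for k = 2, 12/15 = 0.800 for k = 3 and 10/15 = 0.667 for k = 5. The mean is 13%, 20% or 33% smaller, whatever the true change. If dropouts are replaced so that 15 patients have both visits (the Protocol 5.1 plan), the factor is 15/(15 + k): 17% smaller for k = 3 and 25% for k = 5.

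The added zeros also tighten the interval. As an assumed example, take m = +3.0 points and SD 4.0 in the patients observed at both visits, with n = 15:

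| k | Both visits observed: mean (95% CI) | LOCF: mean (95% CI) |
|---|---|---|
| 2 | 3.0 (0.58 to 5.42) | 2.6 (0.47 to 4.73) |
| 3 | 3.0 (0.46 to 5.54) | 2.4 (0.32 to 4.48) |
| 5 | 3.0 (0.14 to 5.86) | 2.0 (0.05 to 3.95) |

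For k = 3 the half-width falls from 2.54 to 2.08 with no added information.

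**5. Is k of 2 or 3 plausible?** Protocol 2.2 gives 45% one-year survival. At a constant hazard, deaths by Week 12 are 1 − 0.45^(12/52) = 0.168, and 0.168 × 15 = 2.5 patients. This is only a gauge. Protocol 2.2 describes excess mortality in the first months, which would raise it. Protocol 5.4 excludes patients not expected to survive more than 6 months, which would lower it. Other withdrawals are not counted.

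**The case against.** Five points can be made against this.

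- **The method is stated in the singular.** SAP 9.2.4.1 most clearly invokes multiple imputation, which is the main method and does not insert zeros. A reader might infer from the LOCF arithmetic that the main result is pulled towards zero. The documents do not support that: the (n − k)/n factor belongs to a sensitivity analysis, and no size has been shown for multiple imputation.
- **If the whole set of methods is meant, Observed Cases is part of it.** An unimputed result may then already be planned. This stands, but the wording does not settle it, and observed cases would still not be the main summary.
- **Exactly 0 is conditional.** Protocol 8.2.5 asks, where possible, for the Follow-Up assessments at an End of Study Visit for withdrawn patients, and Protocol 4.2.1 treats EOS and FU as one label. If that score is held as Follow-up, the LOCF change need not be 0, although it still rests on an imputed Week 12. It also means that Week 13 is not necessarily the only off-treatment look at a lesion. The SAP text between Sections 8.4 and 8.6 was not available for this review, so a visit-allocation rule there cannot be excluded.
- **Plain observed cases would do harm.** The BWAT total needs all 13 items (SAP 6.6.1), while depth and probing items are optional (Protocol 4.2.1 and 7.5.2). A ban on all imputation would drop patients who were seen at both visits. VAS is a single mark and has no such difficulty. This stands and shapes the fix.
- **Little rides on it.** The analysis is exploratory and only summarised. This stands and sets the severity.

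A reader might also infer that the BWAT and VAS off-treatment results cannot be compared at all. That goes too far, since both have by-visit observed-case summaries. Only the paired Week 12 to Follow-up contrasts differ in basis.

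**Conclusion.** The point holds, as a minor one. As written, SAP 9.2.4.1 reports an off-treatment BWAT change that can include patients with neither visit. The main method generates their scores from a model that does not know they stopped. Under LOCF, if it is applied and no End of Study score fills the Follow-up slot, such patients count as exactly 0, and so do those with Week 12 but no Follow-up. The LOCF mean is then (n − k)/n of the observed mean, 20% smaller for k = 3 of 15. The value of k is assumed, because the documents give no dropout rate. The effect on the multiple-imputation result is unquantified. The primary endpoint and its conclusion are not touched.

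**What to change.** In SAP 9.2.4.1, make the main summary the Week 12 to Follow-up change in patients (for secondary and tertiary lesions, in lesions) with a BWAT assessment actually carried out at both visits, and show n. State that:

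- whole missing visits are not imputed for this contrast;
- an End of Study score taken after early withdrawal does not count as Follow-up here;
- item-level imputation is kept within attended visits, so that an unscored optional item does not remove the patient.

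The change costs one or two SAP sentences. The price is a smaller n and a result openly limited to patients who reached Week 12 and were seen afterwards. Totals with a filled-in item will still carry some imputation.
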